## 5. Study Treatments

### 5.1. Investigational Product

The investigational product (IP) is acoziborole, in 320-mg tablets, administered by the oral route to patients in the fasting state according to the following dosing regimen:

- 960 mg (3 tablets) in a single intake on Day 1.

Acoziborole will be provided by DNDI, [name].

For the course of action in the event of vomiting, see the Investigator Manual.

#### 5.1.1. Treatment Allocation

All patients who give their consent or assent to participate in the study and who fulfil the inclusion and exclusion criteria will be allocated to treatment with acoziborole. In addition, the treatment kits will be numbered, and the number will be recorded in the case report form (CRF).

#### 5.1.2. Labelling and Packaging of IP

The tablets of acoziborole will be packaged in aluminium-aluminium blister packs. Each pack will contain the number of tablets required for one administration, i.e. 3 tablets. The blister pack will be packaged in an individual treatment kit for each patient.

The labelling on the treatment kit will display the following information items:

- Name of Sponsor\*, name and contact details for the Coordinating or Principal Investigator
- Study number\*
- Name\* and dosage strength\* of the IP
- Dosage form\*, route of administration\*, number of dosage units\*
- Instructions for use
- Statements “For clinical study use only”\* and “Keep out of reach of children”

- Batch number\* and number of treatment kit\*
- Expiry date and storage conditions

The information items marked with an asterisk (\*) will also be displayed on the immediate packaging of the IP.

Information on acoziborole will be provided in the Investigator Brochure attached to the protocol submitted to the National Authorities.

### **5.1.3. Accountability of IP**

Study-specific forms must be used for accountability of acoziborole. Appropriate records concerning receipt, use, return, loss or any other disposition of acoziborole must be maintained by the Investigators at the investigational centre, or by their delegates, under the supervision of the Principal Investigator. In addition, the study monitors must check accountability of acoziborole during their on-site monitoring visits.

In the investigational centres, acoziborole must be stored in a locked room, or a locked cabinet if no specific room is available, with access limited to the nurse in charge of the pharmacy or to authorised study personnel.

The IP, acoziborole, must not be used for purposes other than the present protocol. The Investigator and the study personnel may not under any circumstances provide other investigators or healthcare services with the acoziborole attributed to their centre, or allow acoziborole to be used other than as described in this protocol without prior written approval from DNDI.

### **5.1.4. Storage of IP**

The IP, acoziborole, must be transported and stored at a temperature not exceeding 30°C. It is recommended to store acoziborole at room temperature. Long-term stability studies showed that the 320-mg tablets of acoziborole, packaged in aluminium-aluminium blister packs, were stable for at least 24 months at 30°C under very humid conditions (75%) and for 6 months at 40°C.

The storage conditions, including the temperature, at the investigational centres must be monitored by the study personnel, and appropriate records must be available.

### **5.1.5. Blinding and Procedure for Unblinding**

This is an open-label study. Thus, the patients and the Investigators will necessarily know which treatment is administered.

## 5.2. Concomitant Treatment

### 5.2.1. Malaria

All patients will undergo a test to detect malaria. All patients with a positive thick smear and/or rapid diagnostic test (RDT) will receive treatment.

Prior to administration of acoziborole, malaria will be treated with Coartem® unless the patient has personal contraindications, such as severe malaria or hypersensitivity to one of the components, i.e. artemether or lumefantrine. All of the existing artemisinin-based combination therapies used against malaria have effects on the QT interval. Coartem® was chosen because its effects on QT-interval prolongation are known to be moderate and well quantified (8).

In patients with a contraindication to Coartem®, the Investigator can choose another antimalarial agent. The choice must be recorded in the CRF.

Treatment will be followed by a recovery period of at least 3 days between the last dose of the antimalarial agent and the administration of acoziborole.

### 5.2.2. Helminthiasis

Treatment for helminthiasis, with mebendazole or albendazole, will be provided free of charge by the Sponsor.

This prophylactic treatment will be given to all patients in the study and will be followed by a recovery period of at least 3 days between the last dose of the antihelminthic agent and the administration of acoziborole.

### 5.2.3. Contraception

Preclinical studies showed that acoziborole has no effect on fertility or on postnatal development (cf. Investigator Brochure). However, because acoziborole has never been administered to women of child-bearing potential, women, as well as men, of reproductive age will be advised to have protected sexual relations during the observation period and up to the 3-month visit. Contraceptive methods, i.e. hormonal contraception and/or condoms, will be available to patients free of charge throughout the duration of their participation in the study.

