## 1.8. Choice of the Dose and Dosing Regimen

The dose of 960 mg was chosen as the therapeutic dose because it ensures exposure levels in the CSF 1.5-fold higher than the pharmacologically active levels at which a 100% trypanocidal effect was obtained in infected animals. In healthy volunteers, plasma levels remained above the effective concentration up to 69 days after the administration of acoziborole.

No safety signals were observed at 1200 mg, which was the highest dose tested in humans. This provides a safety margin approximately 1.5- to 3-fold higher than the no observed adverse effect level in animals.

No studies have been performed on the effect of food on the bioavailability of acoziborole and, for this reason, the single dose of the investigational product must be taken in the fasting state.

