**Table 2 - Theoretical Schedule of Visits and Acceptable Leeway**

Theoretical schedule of visits	Ideal timing of visits	Acceptable leeway*
End-of-hospitalisation (EoH) visit	Between D13 and D18 after D1	D18 at the latest
3 months	3 months $\pm$ 1 week after D1	2-4 months after D1
6 months	6 months $\pm$ 2 weeks after D1	5-9 months after D1
12 months	12 months $\pm$ 4 weeks after D1	10-16 months after D1
18 months	18 months $\pm$ 4 weeks after D1	17-21 months after D1

\* The acceptable leeway for the visit starts on the first day of the period mentioned and ends on the last day of the period mentioned.

Any additional unscheduled visits that may take place must be recorded in the CRF.

In addition to this study, patients will be invited to participate in a prospective study, DiTECT-HAT-WP4, the aim of which is to assess tests to predict the efficacy of treatment of HAT. If the patient declines the invitation to participate in the DiTECT-HAT-WP4 study, this will have no effect on his/her participation in the study on acoziborole or on the care s/he receives. For patients who accept the invitation to participate in the DiTECT-HAT-WP4 study, and only for these patients, additional blood (+ 2.5 mL) and CSF (+ 2.5 mL) samples will be collected at the same time as samples are collected in the present study, i.e. at

baseline, on D11 and at the follow-up visits at 6 months, 12 months and 18 months, to avoid subjecting the patient to additional invasive procedures.

See also Table 6 - Schedule of Procedures (Appendix 4 p89).

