### 6.3. Other secondary efficacy endpoints

#### Time to proven and definitive failure in Patients with Stage 2 HAT

The starting point is administration of acoziborole. The time of failure is the time of the first objective evidence of sustainable failure defined as:

- Death for any reason (at any time on or after administration of acoziborole)
- Decision to use rescue medication (at any time on or after administration of acoziborole)
- Observation of trypanosomes in any body fluid at M6, M12 or M18
- a CSF WBC above 50 / $\mu$ L at 6 months followed by a confirmation of failure defined as:
  - CSF WBC above 20 / $\mu$ L at 12 months, and/or
  - CSF WBC above 20 / $\mu$ L at 18 months, and/or
  - Sign and symptoms evoking a relapse at M12, and/or
  - Sign and symptoms evoking a relapse at M18.
- a CSF WBC above 20 / $\mu$ L at 12 months followed by a confirmation of failure defined as:
  - CSF WBC above 20 / $\mu$ L at 18 months, or
  - Sign and symptoms evoking a relapse at M18.
- a CSF WBC above 20 / $\mu$ L at 18 months

This endpoint will be derived as follows:

- Proven and definitive failure patients:
  - Event (cf. definition above)
  - Time = Theoretical time of the follow-up visit (i.e. day 15 for EoH visit, day 91 for M3 visit, day 183 for M6 visit, day 365 for M12 visit, day 548 for M18 visit)
- Non-failure patients (i.e. proven and definitive failure free):
  - If CSF WBC > 20/ $\mu$ L at 12 months and CSF WBC < 20/ $\mu$ L at 18 months:
    - Censoring at M12 visit
    - Time = Theoretical time of M12 visit (i.e. at day 365)
  - Otherwise:
    - Censoring at the last visit free from proven and definitive failure
    - Time = Theoretical time of the follow-up visit (i.e. day 15 for EoH visit, day 91 for M3 visit, day 183 for M6 visit, day 365 for M12 visit, day 548 for M18 visit)

Note: Unlike the preceding endpoints, a patient cannot be a proven and definitive failure at a given time point and a success at a subsequent endpoint. Consequently, a patient with a CSF WBC above 20/ $\mu$ L at 12 months and below 20/ $\mu$ L at 18 months will be censored at 12 months. A patient lost to follow-up is a patient censored at the last available visit if there is no evidence of failure up to the last available visit. A success at 18 months (last assessment) is a patient censored at 18 months, i.e. with no evidence of failure up to 18 months.

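### Contraception advice ends at the 3-month visit with no minimum time since dosing, and that visit is accepted from 2 months after dosing, so the advice can stop about a month early

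*Protocol*

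**What the plan says.** Section 5.2.3 of the protocol states that men and women of reproductive age will be "advised to have protected sexual relations during the observation period and up to the 3-month visit". Its stated reason is precautionary: the advice is given "because acoziborole has never been administered to women of child-bearing potential". The same section reports that "Preclinical studies showed that acoziborole has no effect on fertility or on postnatal development" and that contraceptive methods "will be available to patients free of charge throughout the duration of their participation in the study".

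Follow-up visits are timed from D1, the day of the single dose (sections 5.1 and 6.1). Table 2 gives the 3-month visit an ideal timing of 3 months ± 1 week and an acceptable leeway of "2-4 months after D1". The footnote says how to read the lower end: "The acceptable leeway for the visit starts on the first day of the period mentioned".

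The plan gives this visit a nominal day in two places. Footnote 6 to the schedule of events (protocol, Appendix 4) uses D90 for PK sampling. SAP section 6.3 uses "day 91 for M3 visit".

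On persistence of the drug, section 1.6 reports a half-life of about 400 hours in healthy male volunteers. Section 1.8 says that "plasma levels remained above the effective concentration up to 69 days after the administration of acoziborole".

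**The concern.** The advice is a precaution against conception while the drug may still be present. Exposure depends on time since the dose, whereas the end of the advice depends on when the patient happens to attend. Because the accepted window opens a full month before the nominal time, a patient who follows the protocol can be released about a month early. Nothing else in the supplied text sets a floor.

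Neighbouring sections do set one where timing around the dose matters: 5.2.1 and 5.2.2 each require at least 3 days between the pre-treatment and acoziborole. Section 5.2.3 has no counterpart.

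What is at stake is a possible conception closer to dosing than the protocol appears to intend. No efficacy endpoint, analysis or eligibility rule is affected.

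**Working it through.** The plan contains no calculation of its own for this point, so the check is date arithmetic on its stated times.

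**Inputs**
- End of advice: the 3-month visit (5.2.3).
- Earliest accepted visit: 2 months after D1, first day included (Table 2 and footnote).
- Nominal visit: D90 (Appendix 4) or day 91 (SAP 6.3).
- Ideal window: 3 months ± 1 week (Table 2).
- Time above the effective plasma concentration: up to 69 days (1.8).
- Half-life: about 400 h (1.6).

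**Calendar lengths**, over all D1 dates from 2016 to 2020, in elapsed days after D1:
- 2 months = 59 to 62 days.
- 3 months = 89 to 92 days.
- For the same D1, 3 months minus 2 months = 28 to 31 days.

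With D1 counted as day 1 and no day 0, the earliest accepted visit falls on study day 59 + 1 = 60 to 62 + 1 = 63.

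**How early the advice can end**

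| Reference time | Arithmetic | Days early |
|---|---|---|
| D90 (protocol) | 90 − 63 to 90 − 60 | 27 to 30 |
| Day 91 (SAP) | 91 − 63 to 91 − 60 | 28 to 31 |
| 69 days after the dose | 69 − 62 to 69 − 59 | 7 to 10 |

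**Visits in the ideal window.** The earliest is 89 − 7 = 82 to 92 − 7 = 85 days after D1. That is at most 7 days short of 3 months and 82 − 69 = 13 to 85 − 69 = 16 days beyond the 69-day mark. The shortfall therefore comes from the wide leeway and not from the ± 1 week window.

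**Persistence, for orientation only.** This assumes first-order elimination with half-life 400 / 24 = 16.7 days and an average month of 365.25 / 12 = 30.44 days. Fraction remaining = 0.5^(t / 16.7):
- At 2 months: t = 60.9 days, 3.65 half-lives, about 8% remaining.
- At 3 months: t = 91.3 days, 5.48 half-lives, about 2% remaining.

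Neither the 69 days nor these fractions is a reproductive-safety threshold. The first supports the dose, both rest on data from men, and the protocol links neither to contraception. The core point needs only section 5.2.3 and Table 2.

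**The case against.** The strongest reply is that no error has been shown. Section 5.2.3 gives a clear end point, no passage contradicts it, and the protocol never states a 3-month duration. D90 is a PK sampling label and day 91 a fixed time for the Kaplan-Meier analysis; neither was written as a contraception period. The early release arises only outside the ideal window, and SAP section 7.5 describes the section 6.1 windows as operational. The same leeway runs to 4 months, so the advice can also last about a month longer than 3 months.

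The risk is managed in other ways too: the preclinical statement, free contraceptives, pregnancy tests at 3 and 6 months, and follow-up of any pregnancy and newborn (6.5.8). Ending the advice at a visit has practical sense, since that visit includes a pregnancy test and face-to-face contact. Finally, the patient information, Investigator Manual and Investigator Brochure are not available here and could state a fixed period.

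Most of this stands as a limit on the size of the effect. It does not remove the gap. A longer precaution in one patient does not make up for a shorter one in another. Availability of contraceptives is not advice to use them, and a pregnancy test detects and does not prevent. The protocol reports the reassuring preclinical findings and then gives the advice anyway. None of the safeguards extends the advice for a patient who attends early.

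**Conclusion.** The point holds as a minor gap in drafting, worth correcting because correction is so cheap. A protocol-compliant patient can be released from the contraception advice 59 to 62 days after dosing, 27 to 31 days before the plan's nominal time for the visit.

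The conclusion assumes that the advice was meant to last about 3 months, which is inferred from the visit's name and nominal day. It also assumes that no unseen document sets a fixed period. The documents do not say how many visits occurred early; the number may be small or zero. No harm to any patient is shown, and no exposure level relevant to pregnancy is given from which a risk could be estimated.

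**What to change.** In section 5.2.3, replace the visit-only end point with: *until the 3-month visit and for at least 3 months after administration of acoziborole (D1), whichever is later*. Bring the patient information into line if it differs.

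The cost is one sentence. No new procedure or supply is needed, because contraceptives are already provided for the whole of participation. The added burden is 28 to 31 more days of advice for a patient seen at the earliest accepted date, at most 7 days for a visit in the ideal window, and none for a visit at or after 3 months. One small drawback is that, for an early attender, the advice would end on a date with no visit attached, so the end date should be given to the patient at the 3-month visit.

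SAP version 4.0 is dated March 2021, so many or all patients may already be past month 3. In that case the wording should be carried into later acoziborole protocols.

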## 5.3. Other Medication

If the patient requires treatment during the first 6 months after administration of acoziborole, the Investigator should be informed and approve the proposed medication. Any medication used after inclusion in the study and/or during the first 6 months of the follow-up period must be recorded in the CRF, specifying the reason for use.

Any medication used to treat an SAE during the follow-up period must be recorded in the CRF (see Section 6.5 Safety Assessments, Definitions and Collection of Adverse Events; p48) and on the SAE reporting form. Any

medication used to treat other non-serious medical events will be recorded only in the patient's medical file.

Any essential medicine required during the 18-month follow-up period will be provided to the patient free of charge. The WHO List of Essential Medicines will be used as a reference guide for the treatment of any concomitant condition (see Investigator Manual). For any chronic condition, the study team will take all necessary measures to ensure that the patient is referred to the most appropriate healthcare facility in the region.

#### **5.4. Rescue Treatment**

In the event of a relapse and after discussion with the Principal Investigator, the patient will receive first-line rescue treatment with NECT or pentamidine, depending on the stage of the disease.

Rescue treatment for HAT will be recorded as rescue treatment in the CRF on the end-of-study page.

Probable relapse at the 6-month, 12-month or 18-month follow-up visit is defined as shown in Table 1.

**Table 1 - Clinical Classification of Patients**

Visit	Ideal timing of visit after end of treatment	Favourable outcome	Uncertain outcome	Probable relapse	Proven relapse
D11	$\pm 1$ day	
 
Patient alive with no evidence of trypanosomes in any body fluid (23)
 
			
 
Evidence of trypanosomes in any body fluid
 

3 months	3 months $\pm 1$ week	
 
Patient alive with no evidence of trypanosomes in any body fluid (no lumbar puncture at 3 months unless Investigator suspects a relapse)
 
	
 
Any reason prompting the Investigator to request an additional follow-up visit
 
	
 
Neurological signs or symptoms leading to use of rescue treatment
 
	
 
Evidence of trypanosomes in any body fluid
 

6 months	6 months $\pm 2$ weeks	
 
Patient alive with no evidence of trypanosomes in any body fluid and CSF WBC <math>\leq 20/\mu\text{L}</math>
 
	
 
CSF WBC between 20 and <math>50/\mu\text{L}</math> and additional visit requested within 1-3 months
 
Any reason prompting the Investigator to request an additional follow-up visit
 
	
 
CSF WBC <math>\geq 50/\mu\text{L}</math>
 
Neurological signs or symptoms leading to use of rescue treatment
 
	
 
Evidence of trypanosomes in any body fluid
 

12 months	12 months $\pm 4$ weeks	
 
Patient alive with no evidence of trypanosomes in any body fluid and CSF WBC <math>\leq 20/\mu\text{L}</math>
 
CSF WBC between 20 and <math>50/\mu\text{L}</math>, and lower as compared to prior value(s)
 
	
 
CSF WBC <math>> 20/\mu\text{L}</math> and non-significant increase from a clinical standpoint in relation to prior value(s)
 
Any reason prompting the Investigator to request an additional follow-up visit
 
	
 
CSF WBC <math>> 20/\mu\text{L}</math> and significant increase from a clinical standpoint in relation to prior value(s)
 
Neurological signs or symptoms leading to use of rescue treatment
 
	
 
Evidence of trypanosomes in any body fluid
 

18 months	18 months $\pm 4$ weeks	
 
Patient alive with no evidence of trypanosomes in any body fluid and CSF WBC <math>\leq 20/\mu\text{L}</math>
 
Patient with no signs of HAT and who refuses to undergo lumbar puncture and who, in the opinion of the Investigator does not require rescue treatment or an additional follow-up visit
 
	
 
Any reason prompting the Investigator to request an additional follow-up visit
 
	
 
CSF WBC <math>> 20/\mu\text{L}</math>
 
Neurological signs or symptoms leading to use of rescue treatment
 
	
 
Evidence of trypanosomes in any body fluid
 

Any discrepancy between the clinical features and laboratory findings may also be an uncertain outcome, or any situation that leads the Investigator or the study team to consider that an additional follow-up visit is required to decide whether or not to provide rescue treatment.

## 6. Schedule of Study Procedures and Assessments

### 6.1. Timing of Assessments

Study procedures will be performed in accordance with the following schedule:

- D-15 to D-1: pre-screening, screening and baseline assessment
- D1: treatment day
- D1 to D15: observation period at hospital
- D11: initial assessment of treatment effect (lumbar puncture)
- D15: end-of-hospitalisation (EoH) visit
- Out-patient follow-up visits at 3 months, 6 months, 12 months and 18 months (see Table 2 – Theoretical Schedule of Visits and Acceptable Leeway). The timing of follow-up visits is calculated from D1.

**Table 2 - Theoretical Schedule of Visits and Acceptable Leeway**

Theoretical schedule of visits	Ideal timing of visits	Acceptable leeway*
End-of-hospitalisation (EoH) visit	Between D13 and D18 after D1	D18 at the latest
3 months	3 months $\pm$ 1 week after D1	2-4 months after D1
6 months	6 months $\pm$ 2 weeks after D1	5-9 months after D1
12 months	12 months $\pm$ 4 weeks after D1	10-16 months after D1
18 months	18 months $\pm$ 4 weeks after D1	17-21 months after D1

\* The acceptable leeway for the visit starts on the first day of the period mentioned and ends on the last day of the period mentioned.

Any additional unscheduled visits that may take place must be recorded in the CRF.

In addition to this study, patients will be invited to participate in a prospective study, DiTECT-HAT-WP4, the aim of which is to assess tests to predict the efficacy of treatment of HAT. If the patient declines the invitation to participate in the DiTECT-HAT-WP4 study, this will have no effect on his/her participation in the study on acoziborole or on the care s/he receives. For patients who accept the invitation to participate in the DiTECT-HAT-WP4 study, and only for these patients, additional blood (+ 2.5 mL) and CSF (+ 2.5 mL) samples will be collected at the same time as samples are collected in the present study, i.e. at

baseline, on D11 and at the follow-up visits at 6 months, 12 months and 18 months, to avoid subjecting the patient to additional invasive procedures.

See also Table 6 - Schedule of Procedures (Appendix 4 p89).

